#### 7.1.2.2 To predict kidney mass stage using 3D CEUS-generated metrics

Based on our clinical experience, we estimate 15 patients will have a T2a category or lower lesion and 25% of those will have a change from clinical to pathological staging. A sample size of 15 patients will not have sufficient power to detect areasonable effect size but computation of parameter estimates and standard errors will inform larger future studies.

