#### 7.2.3 Predicting kidney mass stage using 3D CEUS-generated metrics

*Image Eligibility:* CEUS mass images from individuals with clinical stage T2a or lower tumors will be eligible for this sub-analysis. We estimate that 15 tumors will meet these criteria since over 50% of kidney cancer resections at UNC are for T2a or lower clinical stage tumors.

*Imaging Procedure and Analysis:* We will use Matlab (Mathworks, Natick, MA) to measure WI and WO rates from TIC analyses. We will apply the 3D volume rendering exploratory analyses described in the primary outcome to this outcome measure. Qualitative interpretation of 3D volume renderings will be assessed and compared to the clinical outcome.

*Gold Standard Comparator:* We will compare the gold standard of postsurgical pathologic stage to WI/WO rates generated from CEUS TICs.

Statistical Analysis: We will use the continuous variables of WI and WO to predict the binary outcome measure of pathologic stage T3 disease or greater. We will calculate means (standard deviations) and 95% confidence intervals for WI and WO for those  $\geq$  stage T3 vs. < stage T3, and compare via t-tests at alpha=.05. We will use logistic regression to assess ability of WI and WO to predict stage T3 disease or greater, both separately and together. We will obtain nonparametric estimates of AUC along with 95% confidence intervals for WI alone, WO alone, and WI and WO combined using the fitted logistic regression models. We will also add patient specific factors to the logistic regression models, to assess the added value of the WI and WO measurements, with analyses to include tests of the effect parameters from the fitted logistic regression models and estimates and confidence intervals for AUCs from those models.

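### In section 7.2.3 the staging data both choose the direction of wash-in and wash-out and score it, so the single-metric AUCs are biased upward when the metrics are weak

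*Combined protocol and SAP*

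**What the plan says.** Section 7.2.3 (Statistical Analysis) uses WI and WO to "predict the binary outcome measure of pathologic stage T3 disease or greater". The modelling step reads: "We will use logistic regression to assess ability of WI and WO to predict stage T3 disease or greater, both separately and together". AUCs follow, described as nonparametric, with "95% confidence intervals for WI alone, WO alone, and WI and WO combined using the fitted logistic regression models". Patient factors are then added to the models, and AUCs with intervals are reported for those models too.

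The section does not say whether higher or lower WI or WO is expected in pT3 disease. The group comparison ("compare via t-tests at alpha=.05") gives no direction either. No cross-validation, optimism correction or separate data set is described for these AUCs. The only bootstrap in the plan is in 7.2.2, for the standard error of the bolus-infusion AUC difference. Section 7.2.2 says it follows the primary objective's modelling strategy; 7.2.3 does not, so a correction made in 7.2.1 would not carry over.

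On size, 7.2.3 says "We estimate that 15 tumors will meet these criteria", and 7.1.2.2 expects that "25% of those will have a change from clinical to pathological staging". Section 7.1.2.2 concedes that power is insufficient and gives the purpose of the analysis: "computation of parameter estimates and standard errors will inform larger future studies".

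**The concern.** An empirical AUC for one continuous metric needs no model, only a stated direction. Taking it from a fitted one-predictor logistic model replaces the metric by its fitted probability, whose order depends on the sign of the estimated slope. That sign follows the observed difference in means between the two outcome groups. When a useless metric happens to point the other way in the sample, the fit turns it round and an AUC below 0.5 becomes one above 0.5.

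No variable selection is involved. The bias comes only from the free choice of sign, and it is largest where the metric is weakest. At stake is the use the plan names for this analysis, which is informing later studies. A planner who sees an AUC near 0.64 for WI could take it as a modest signal when it is about what no information would produce.

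**Working it through.** **No plan figure to reproduce.** The documents give no expected AUC, null AUC or numerical power for the staging analysis.

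**Inputs.**
- Tumours: 15 (7.1.2.2 and 7.2.3).
- Events: 15 x 0.25 = 3.75, taken as 4 against 11 others. This assumes that every stage change is to pT3 or higher. The documents do not say so, hence the range of splits below.

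**Step 1: what the fitted model does to the AUC.** Let A be the empirical AUC of the raw metric with higher values read as pT3 or higher. The AUC of the fitted probabilities is A if the slope is positive and 1 - A if it is negative. In 8,000 fitted logistic models the slope sign matched the sign of the mean difference every time.

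**Step 2: size under no information, by hand.** With m events and n non-events, A has mean 0.5 and SD = sqrt[(m + n + 1)/(12mn)]. If the data always chose the favourable side, the normal approximation gives E[max(A, 1 - A)] = 0.5 + SD x sqrt(2/pi).
- At 4 vs 11: SD = sqrt(16/528) = 0.174, so 0.5 + 0.174 x 0.798 = 0.639. Exact enumeration of the ranks gives 0.641.

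This is an upper figure for the plan's estimator. The slope follows means rather than ranks, so the fit does not always land on the favourable side.

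**Step 3: the plan's own estimator.** Simulated mean AUC of a useless metric, direction set by the slope sign:

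| Events vs others | Exact upper figure | Normal metric | Lognormal metric |
|---|---|---|---|
| 5 vs 10 | 0.632 | 0.627 | 0.606 |
| 4 vs 11 | 0.641 | 0.635 | 0.616 |
| 3 vs 12 | 0.656 | 0.651 | 0.631 |
| 2 vs 13 | 0.685 | 0.681 | 0.658 |

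Actual logistic fits with a normal metric gave 0.636 at 4 vs 11 and 0.652 at 3 vs 12. With a direction fixed in advance the expectation is 0.50 in every row.

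**Step 4: chance of an encouraging result.** At 4 vs 11, about 28% of useless metrics show an AUC of 0.70 or more. With a fixed direction, symmetry halves this to about 14%.

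**Step 5: metrics that carry information (4 vs 11, normal).** A true AUC of 0.60 averages 0.656, 0.70 averages 0.717, and 0.80 averages 0.803.

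**Step 6: WI and WO together.** With neither informative, fitted two-metric models average 0.714 at 4 vs 11 and 0.737 at 3 vs 12. Models adding patient factors spend more parameters on the same patients; they were not simulated.

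**Step 7: intervals.** The plan names no interval method, so DeLong intervals are an assumption here. At 4 vs 11 with no information:
- Fixed direction: about 5.7% lie wholly above 0.5 and about 5.7% wholly below, total about 11%.
- Slope-chosen direction: about 11% lie wholly above and essentially none below, total about 11%.

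At 2 vs 13 the total is about 25% either way; the share wholly above rises from about 12% to about 25%.

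**The case against.** Several points on the other side are sound and limit the claim.

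- **Intervals.** A reader might infer that the flip makes the confidence intervals exclude 0.5 too often. It does not. The interval for 1 - A mirrors that for A, so total exclusion is unchanged. The excess over 5% is small-sample behaviour of the assumed DeLong method, which fixing the direction would not cure. The flip only moves the errors to the favourable side.
- **Values near 0.5.** A reader might also infer that these AUCs cannot sit near 0.5. At 4 vs 11 with a normal metric, about 43% of useless metrics land between 0.40 and 0.60, and about 6% fall below 0.5 (about 16% if lognormal).
- **Size against noise.** Even under no information the shift (0.135) is smaller than one standard deviation of the raw AUC (0.174), and for good metrics it is negligible.
- **Other outputs.** Group means, t-tests and logistic coefficients keep their sign and are unaffected. If the slope sign is reported, a reader can recover the raw AUC. The stated purpose refers to parameter estimates and standard errors and does not name AUCs.
- **Wording.** The phrase about fitted models might be meant mainly for the combined model. As written, though, it also covers WI alone and WO alone.
- **Low power is admitted.** That concerns imprecision. It does not warn of a systematic upward shift in an estimate reported with an interval.

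What survives is the bias in the reported AUCs, concentrated on weak metrics.

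**Conclusion.** The concern holds for the point estimates. As written, 7.2.3 lets the same patients set and score the direction of WI and WO. At 4 vs 11 a useless metric averages about 0.62 to 0.64 instead of 0.50, depending on skewness; for normal data the figure is about 0.65 at 3 vs 12 and 0.68 at 2 vs 13. The two-metric model starts from about 0.71. These sizes rest on 15 tumours, on an event count the documents do not give, and on the simulated distributions. If some stage changes are not to pT3 or higher, events are fewer and the bias is larger.

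This is a secondary analysis conceded to be underpowered, with no AUC threshold or decision attached. The change should be made because it is cheap and these AUCs may be carried into later planning. It does not threaten the primary objective.

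**What to change.** In 7.2.3, state that the AUCs for WI alone and WO alone are the empirical AUCs of the raw metrics, each in one direction fixed before pathology outcomes are seen, and that values below 0.5 will be reported as they fall. The documents support neither direction, so the investigators must choose and record one for each metric; even an arbitrary choice removes the bias.

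For the WI plus WO model and the models adding patient factors, report optimism-corrected AUCs (for example leave-pair-out), or label them apparent and not for planning. Name the interval method. The logistic models stay for the tests of effect.

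The cost is a few lines of text, no new data and little extra computation. The downside is that reported AUCs will be lower and some may fall below 0.5. Small-sample interval coverage remains a separate limitation.

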# 7.0 STATISTICAL CONSIDERATIONS

#### 7.1 Sample Size and Accrual

We will enroll 25 adult subjects with suspected with suspected kidney cancer and planned surgical nephrectomy. We have deep recruitment experience for kidney CEUS imaging. Approximately 150 nephrectomies for localized disease are performed at UNC yearly. Based on our previous recruitment rate of ~75% and a strong partnership with our urology colleagues, we anticipate no problems meeting our recruitment goal of 25 subjects.

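### Section 7.2.3 adds patient factors to the WI and WO staging models by ordinary logistic regression with at most about 3.75 expected pT3-or-higher events; with several factors the model usually has no finite estimate

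*Combined protocol and SAP*

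**What the plan says.** Section 7.1.2.2 sizes the staging objective: "we estimate 15 patients will have a T2a category or lower lesion", and "25% of those will have a change from clinical to pathological staging". It concedes that 15 patients are too few for adequate power, but keeps the analysis because "computation of parameter estimates and standard errors will inform larger future studies".

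Section 7.2.3 sets the outcome and the models. WI and WO are to "predict the binary outcome measure of pathologic stage T3 disease or greater". The core models are named: "We will use logistic regression to assess ability of WI and WO to predict stage T3 disease or greater, both separately and together". Then comes the extension at issue here: "We will also add patient specific factors to the logistic regression models, to assess the added value of the WI and WO measurements". Parameter tests and AUCs with confidence intervals are to be taken from those extended models.

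The section also plans group means, SDs, confidence intervals and t-tests for WI and WO. It does not say which patient factors enter, how many, or whether they enter together. Neither section gives an expected number of pT3-or-higher events, a penalised or exact method, a limit on predictors, or a rule for separation or non-convergence.

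**The concern.** A logistic model has finite maximum-likelihood estimates only if no linear combination of the predictors separates events from non-events, completely or with ties (quasi-complete separation). With very few events and several slopes, separation is common even when no predictor is related to the outcome. Software then stops at an arbitrary large coefficient with a huge standard error, and the Wald test says nothing.

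This differs from low power. Low power gives wide but usable estimates; separation gives no finite estimate. The admission in 7.1.2.2 covers the first and not the second, because it still relies on the estimates and standard errors for planning. Two things are at stake: the planning value of the added-value analysis, and the risk that a fitted AUC at or near 1 is read as staging ability.

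**Working it through.** **The plan's sample.** Section 7.1 states "We will enroll 25 adult subjects", and 7.2.3 notes that "over 50% of kidney cancer resections at UNC are for T2a or lower clinical stage tumors". 25 x 0.50 = 12.5, so at least about 13 patients. The stated 15 is 15/25 = 60%, which is consistent.

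**Expected events.** Every eligible patient is clinical T2a or lower, so a pT3-or-higher result is always a stage change. The reverse does not hold: read literally, a change within T1-T2 or a downstaging counts in the 25% but is not an event. Hence expected events <= 15 x 0.25 = 3.75. If all changes were to pT3 or higher, the count would be Binomial(15, 0.25), with P(5 or more) = 31% and P(0 or 1) = 8%.

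**Slopes.** WI, WO, age, sex and race (one slope each, race as two categories) make five. Events per slope are 3.75/5 = 0.75. The factor list is assumed from Table 1 of the primary analysis.

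**How often the estimate fails to exist.** Data sets were simulated and tested for complete or quasi-complete separation by linear programming. The settings below are assumptions, since the documents give no values:
- n = 15, with 3 or 4 events;
- WI and WO normal with correlation 0.5;
- pT3 group shifted by 0, 0.8, 1.2 or 1.8 SD on each marker;
- age, sex and race unrelated to the outcome, with sex/race prevalence 35%/25% or 50%/50%;
- 300 data sets per setting (Monte Carlo error up to about 6 points).

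| Model | Slopes | No finite estimate, 3-4 events, shifts 0-1.8 SD |
|---|---|---|
| WI alone | 1 | 0-21% |
| WI + WO | 2 | 1-53% (1-4% with no effect; 8-22% at 0.8-1.2 SD; 44-53% at 1.8 SD) |
| WI + WO + age | 3 | 4-73% (4-44% up to 1.2 SD) |
| WI + WO + age + sex | 4 | 25-87% |
| WI + age + sex + race | 4 | 33-87% |
| WI + WO + age + sex + race | 5 | 48-96% (48-93% at 4 events; 66-96% at 3) |

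With event counts drawn from Binomial(15, 0.25), the five-slope model fails in 60-94%. A separate simulation limited to shifts of 0-1 SD gave 56-71% at 4 events and 74-87% at 3 for that model, against 0-3% for WI alone and 1-15% for WI + WO. Failure becomes more frequent as the markers become stronger.

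**Where the estimate exists.** The median standard error of the WI log odds ratio per SD is about 0.7-1.2 (WI alone), 0.9-1.6 (WI + WO) and 1.2-2.0 (five slopes).

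**Maximum likelihood against Firth** (4 events, 0.8 SD shift on both markers, 600 runs). In the five-slope model, the standard error for WI exceeded 10 in 55% of maximum-likelihood fits (median about 1,100) and in 0% of Firth fits (median 0.87). In WI + WO the figures were 9% and 0%.

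**AUC.** With five slopes, 4 events and no true effect, 53% of data sets were separated but only 31% completely. Under Firth in the same setting the mean in-sample AUC was 0.87, and it equalled 1 in 19% of runs.

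**The case against.** The strongest reply is that the five-slope model is an assumption. Section 7.2.3 names only WI, WO and WI + WO, and leaves the patient factors open. If they were added singly, as in WI + WO + age, failure stays below half for shifts up to 1.2 SD. This stands, and it limits the point to models with several factors. It does not clear the plan, because nothing in 7.2.3 prevents joint entry and the only list of patient factors in the document has three.

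A reader might infer that all the staging models break down and that the objective yields nothing usable. The documents do not support that. The named WI and WO models usually have finite estimates, and the group means, SDs and t-tests need no logistic fit. A rank-based AUC for a single marker does not need one either. All of these are legitimate planning inputs.

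A reader might also infer that the AUC will be 1 whenever the model is separated, or that there can be no more than about 4 events. Neither follows. Quasi-complete separation, such as no event in one race category, need not give an AUC of 1, and 3.75 is an expectation.

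Finally, this is a secondary objective, openly underpowered, with no decision rule attached. That limits the harm but leaves the added-value analysis unworkable if several factors are entered.

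**Conclusion.** The point holds for the added-value models in 7.2.3 when several patient factors enter together. With WI, WO, age, sex and race, and 3 or 4 events in 15 patients, no finite maximum-likelihood estimate exists in roughly 50-95% of data sets. The parameter tests and standard errors planned from that model would then be artefacts. It does not extend to WI alone or WO alone. It reaches WI + WO only if both markers are very strong, at about 1.8 SD each.

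The event bound rests on the plan's 15 patients and 25%. The failure rates rest on the Table 1 factor list and on the assumed correlation, shifts and prevalences, which is why ranges are given. The change should be made, but it concerns one part of a secondary objective and does not touch the primary analysis.

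**What to change.** In 7.2.3:
- Fit the staging models by Firth penalised logistic regression with profile-penalised confidence intervals.
- Name the patient factors and add one prespecified factor at a time, or drop the models with several factors.
- Report AUCs from multi-term models with an optimism correction, or label them as apparent. Firth regression keeps the coefficients finite but does not remove in-sample optimism, as the mean AUC of 0.87 with no true effect shows.

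In 7.1.2.2, state the expected number of pT3-or-higher events (at most about 3.75 on the plan's figures) beside the 25% any-change figure, and say that it is an expectation.

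The cost is SAP wording and a standard software option, with no new patients or procedures. The price is mild shrinkage of the estimates and fewer adjusted models.

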## 8.0 STUDY MANAGEMENT

#### 8.1 Institutional Review Board (IRB) Approval and Consent

It is expected that the IRB will have the proper representation and function in accordance with federally mandated regulations. The IRB should approve the consent form and protocol.

In obtaining and documenting informed consent, the investigator should comply with the applicable regulatory requirement(s), and should adhere to Good Clinical Practice (GCP) and to ethical principles that have their origin in the Declaration of Helsinki.

Before recruitment and enrollment onto this study, the patient will be given a full explanation of the study and will be given the opportunity to review the consent form. Each consent form must include all the relevant elements currently required by the FDA Regulations and local or state regulations. Once this essential information has been provided to the patient and the investigator is assured that the patient understands the implications of participating in the study, the patient will be asked to give consent to participate in the study by signing an IRB-approved consent form.

Prior to a patient's participation in the trial, the written informed consent form should be signed and personally dated by the patient and by the person who conducted the informed consent discussion.

#### 8.2 Registration Procedures

Study participants will be registered into OnCore®, a web based clinical research platform by one of the Study Coordinators.

#### 8.3 Data Management and Monitoring/Auditing

Copies of completed CRFs with subject IDs will stored within subjects' binders and data will be entered in the secure REDCap database. Study personnel will have access to enter data in the study database. Data should be entered in the study database within 5 business days to ensure timely entry.

The coordinator will complete the first CRF together with the PI to verify that it is completed correctly. We will verify a randomly selected 25% of all source documents. The randomization for this verification will be generated using a random number generator in Excel. Source document verification and monitoring will be documented and stored with the regulatory files.

#### 8.4 Adherence to the Protocol

Except for an emergency situation in which proper care for the protection, safety, and well-being of the study patient requires alternative treatment, the study shall be conducted exactly as described in the approved protocol.

#### 8.4.1 Emergency Modifications

UNC investigators may implement a deviation from, or a change of, the protocol to eliminate an immediate hazard(s) to trial subjects without prior UNC's IRB/IEC approval/favorable opinion.

For any such emergency modification implemented, an IRB modification form must be completed by UNC Research Personnel within five (5) business days of making the change.

#### 8.4.2 Single Subject Exceptions

8.4.3 Eligibility single subject exceptions are not permitted for Lineberger Comprehensive Cancer Center Investigator Initiated Trials under any circumstances. Other types of single subject exceptions may be allowed if proper regulatory review has been completed in

# accordance with Lineberger Comprehensive Cancer Center's Single Subject Exceptions Policy. Other Protocol Deviations/Violations

According to UNC's IRB, a protocol deviation is any unplanned variance from an IRB approved protocol that:

- Is generally noted or recognized after it occurs
- Has no substantive effect on the risks to research participants
- Has no substantive effect on the scientific integrity of the research plan or the value of the data collected
- Did not result from willful or knowing misconduct on the part of the investigator(s).

An unplanned protocol variance is considered a violation if the variance meets any of the following criteria:

- Has harmed or increased the risk of harm to one or more research participants.
- Has damaged the scientific integrity of the data collected for the study.
- Results from willful or knowing misconduct on the part of the investigator(s).
- Demonstrates serious or continuing noncompliance with federal regulations, State laws, or University policies.

If a deviation or violation occurs please follow the guidelines below:

**Protocol Deviations:** UNC personnel will record the deviation in OnCore®, and report to any sponsor or data and safety monitoring committee in accordance with their policies. Deviations should be summarized and reported to the IRB at the time of continuing review.

**Protocol Violations:** Violations should be reported by UNC personnel within one (1) week of the investigator becoming aware of the event using the same IRB online mechanism used to report Unanticipated Problems.

